## 2. STUDY SYNOPSIS AND SCHEMA

## Study Synopsis

[figure not shown]
Title	Efficacy of ASIMOMMY® Compared to Domperidone and Placebo in Increasing Breastfeeding: Randomized Single-Blind Controlled Trial in Indonesia.
Purpose	Assessing the efficacy of ASIMOMMY® in increasing breast milk production in postpartum mothers.
Hypothesis	ASI MOMMY® increases milk production in postpartum mothers.
Methodology	
Study Design	Randomized Control Trial (RCT) .
Study Time	October 2022 until March 2022.
Study Location	Tegalrejo and Jetis Primary Health Care, Yogyakarta.
Study Product	
Treatment group	ASI MOMMY®.
Control group:	Domperidone and placebo.
Subject Criteria:	
Inclusion Criteria:	
 
Mothers 20-35 years old.
 
Gestational age at delivery 37-40 weeks.
 
Vaginal delivery.
 
Normal body mass index (BMI 18.5-24.9 kg/m^2).
 
Not taking drugs or breast milk enhancement supplements.
 
Healthy mother's condition with normal nipples (protruding).
 
Healthy baby condition with good suction reflex.
 
The baby consumes only breast milk.
 

Exclusion criteria:	
 
Allergy to ASI MOMMY® and Domperidone.
 
The mother is taking medications that affect the effects of domperidone (such as antacids, cimetidine, ranitidine, famotidine and nizatidine) or medications that interact with domperidone (such as haloperidol, lithium).
 
The mother is in a state of illness requiring hospitalization.
 
Mother has HIV AIDS, heart problems, mastitis, and had undergone breast surgery.
 
Underweight, overweight and obese mothers.
 
Giving birth to twins.
 
The baby has a congenital defect that affects the suctioning process of breast milk
 

	
 
• Infants and mothers who did not participate in the treatment until completion (day 7 of the intervention).
 

Sampel size	The sample size was 15 subjects per group. The total sample size was 45 subjects.
Subject Allocation Method	Randomization with a randomization list.

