Intervention	
 
• Beginning of the study is on day 3 postpartum, the initial baby weight was weighed before the start of the intervention.
 
• The weighing was conducted at Tegalrejo and Jetis Primary Health Center, at 08.00-10.00 WIB using Onemed OD-231 digital baby scales with an accuracy of 0.01 kg. When weighing the baby did not wear clothes or pampers.
 
• Body weight weighing was carried out at Tegalrejo and Jetis Primary Health Center, at 08.00-10.00 WIB using Onemed OD-231 digital baby scales with an accuracy of 0.01 kg. When weighing babies do not wear clothes or pampers.
 
• Intervention starts on the 3rd day postpartum until the next 7 days (10th day postpartum) with drug administration.
 
• The intervention provided will be single-blind, the packaging will be similar, and neither the research assistant nor the subject will know the type of intervention provided. Administration of domperidone in capsule preparation at a dose of 10 mg orally taken every 8 hours, 3 times a day, for 7 days, at 06.00, 14.00, and 22.00 WIB. ASIMOMMY® and placebo in capsule preparation were taken once a day, at night, as much as 2 capsules, for 7 days. Each subject will get all capsules on the first day to be taken for 7 days.
 
• Evaluation of the baby's weight was done by re-weighing the baby's weight on the 7th day of the intervention. Then the baby's weight gain was assessed, which was obtained from the difference between the baby's weight on day 7 of the intervention and the baby's weight on day 0 (before the intervention).
 

Duration of intervention	7 days.
Study Outcomes	Breast milk production was measured by assessing the infant's weight gain, which was obtained from the difference between the infant's weight on day 7 of the intervention and the infant's weight on day 0 (before the intervention).
Statistical Analysis	Statistical data analysis in this study used the SPSS version 24.0 program. Data were tested for normality first to determine the statistical analysis test used next. Research results with categorical data (nominal and ordinal) are displayed in the form of number/frequency and percentage of each group. Numerical data that is normally distributed (parametric) will be displayed in the mean and standard deviation, while if the data is not normally distributed (non-parametric) it is displayed with the median, minimum and maximum values.

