Chi Square test was used for variables with categorical data (nominal and ordinal). The bivariate analysis test used for variables with numerical data (parametric) is One Way Anova with Post Hoc Bonferroni, while for non-parametric is Kruskall Walis with Post Hoc Mann Whitney.

The analysis test for external variables with parametric data and dependent variables was carried out with the Pearson correlation test, while for non-parametric data it was carried out with the Spearman correlation test.

Synopsis or Schema:

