## 8. STUDY DESIGN

### a. Overview of The Study Design

This research is a pilot study, single blind, randomized controlled trial. Subjects are allocated to three groups with a randomized list. The three treatment groups are the intervention group, positive control group, and negative control group. The intervention group is the group of patients that receive ASI MOMMY®, the positive control group are patients that receive domperidone, and the negative control group is the placebo group.

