### 14. STATISTICAL ANALYSIS

a. General Design

The method used in this research is a single blind, Randomized Control Trial (RCT). The benchmark of this study is the measurement of the babies' weight before and after the intervention therapy that is given (the research product).

i. Hypothesis

**H0:** The traditional drug preparation ASIMOMMY® does not increase breastmilk production in postpartum women.

**H1:** The traditional drug preparation ASIMOMMY® increases breastmilk production in postpartum women.

ii. Output (*Endpoint*)

The output expected is that ASI MOMMY® is able to increase the production of breastmilk which in turn increases the weight of the baby after the mother receives the intervention.

b. Rationale for Sample Size and Statistical Power

Sample size is calculated using sample size formula for hypothesis testing on the average of more than two groups, unpaired numeric comparative in one measurement, are as follows (Dahlan, 2016):

$$z_{\beta} = \frac{\sqrt{v_2(2[v_1+\delta^2]^2-[v_1+2\delta^2])} - \sqrt{v_1(v_1 + \delta^2)(2v_2 - 1)F}}{\sqrt{v_1}(v_1 + \delta^2)F + v_2(v_1 + \delta^2)}$$

Information:

$n$  = number of subjects in one group

$Z_{\beta}$  = beta standard value 20 % which is 0,84

$V_1$  = degree of freedom from the number of =  $k-1$ .  $V_1 = 3-1 = 2$

$V_2$  = degree of freedom from the number of groups  $k$  ( $n-1$ ).  $V_2 = 3(n-1)$

$K$  = number of groups = 3

$$\delta^2 = \frac{n \sum (x_i - \bar{x})^2}{s^2}$$

$X_i$  = average of baby body weight in a group

$X_1$  = average of baby body weight in the domperidone and placebo group which is 3426,6 (Amri *et al.*, 2020)

$X_2$  = average of baby body weight in the placebo group which is 3221,1 (Amri *et al.*, 2020)

$X_3$  = average of three groups is 3000

$X$  = overall average (3 group)

$S$  = combined standard deviationn

$F$  = Anova table value as function of type 1,  $V_1, V_2$

Alpha = type 1 error 0,05.

i. Projected Number of Site

Locations used in this study are two sites which are Jetis and Tegalrejo Public Health Centers in Yogyakarta.

ii. Projected Number of Participant per site

Total number of subjects in one place is around 22 or 23 subjects.

c. Statistical Methods for primary and Secondary Outcomes

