Statistical data analysis in this study is done using SPSS 24.0 program. The data undergoes normality testing first to determine which statistical analysis test will be used. The result of research with categoric data will be presented in the form of quantity/frequency and percentage from each group. Numeric data with normal distribution (parametric) will be presented in the form of average and standard deviation, whereas if the data is not distributed normally (non-parametric) then it will be presented using median, minimal value and maximum value.

d. Significance Testing

Chi-squared test is used for variables with categoric data (nominal and ordinal). Bivariate analysis test that is used for variables with numeric data (parametric) is the One Way Anova test with Post Hoc Bonferroni, meanwhile for non parametric data is Kruskall Walis with Post Hoc Mann Whitney.

Analytical test for variables aside from parametric data and dependent variables is using Pearson correlation, while non-parametric data is analysed using Spearman correlation

e. *Demographic and baseline Characteristics*

Research data with categoric data (nominal and ordinal) is presented in the form of quantity/frequency and percentage from each group.

f. *Safety Analysis*

The entire data analysis process will be done by a biostatistics expert appointed by the research team.

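### A normality test on groups of 15 chooses the analysis of the only stated outcome, and the two branches treat the pairwise comparisons differently

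*Protocol*

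**What the plan says.** Section 14.c of the protocol makes the choice of test depend on the data: "The data undergoes normality testing first to determine which statistical analysis test will be used". The synopsis has the same rule: "Data were tested for normality first to determine the statistical analysis test used next". Neither place names the normality test, its level, or what is tested (each arm, all data pooled, or residuals).

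Section 14.d then gives two branches for numeric variables: "One Way Anova test with Post Hoc Bonferroni, meanwhile for non parametric data is Kruskall Walis with Post Hoc Mann Whitney". The synopsis repeats them: "One Way Anova with Post Hoc Bonferroni, while for non-parametric is Kruskall Walis with Post Hoc Mann Whitney". Bonferroni is a correction. Mann-Whitney is only a test, and no level or correction is attached to it in either place.

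The rule governs the only stated outcome, because weight gain from day 0 to day 7 is numeric. On group size, the synopsis says "The sample size was 15 subjects per group".

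The alternative hypothesis in section 14.a is "The traditional drug preparation ASIMOMMY® increases breastmilk production in postpartum women". It names no comparator. The title has ASI MOMMY "Compared to Domperidone and Placebo in Increasing Breastfeeding", and section 8.a says that "the positive control group are patients that receive domperidone, and the negative control group is the placebo group". ASI MOMMY versus placebo is thus the natural test of H1, but no section says so.

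**The concern.** A test of normality on 15 infants per arm is a noisy guide. It sends some truly normal data to the rank branch and leaves some skewed data on the ANOVA branch. Here it settles more than the choice of test. With Bonferroni over three pairs the pairwise threshold is 0.05/3 = 0.0167. On the other branch no correction is named, and a reader would most likely apply the overall alpha of 0.05.

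The same observed advantage of ASI MOMMY over placebo could therefore be declared significant or not according to a preliminary test that has nothing to do with efficacy. Section 14 sets a formal H0 and H1 with alpha 0.05 and beta 20%, so the trial's conclusion rests on this step.

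**Working it through.** **Inputs from the protocol.** Three groups, 15 per group, alpha 0.05, beta 20%. No SD is given, no distribution of weight gain and no named normality test. The group size cannot be reproduced for the same reason: with the listed means (3426.6, 3221.1 and 3000, which are body weights, not gains), 15 per group gives 80% ANOVA power only if the SD is about 363 g. That SD is inferred, not stated, and says nothing about the spread of gains. Effects below are therefore in SD units.

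**Assumptions.** ASI MOMMY exceeds placebo by 0.8 or 1.05 SD, with domperidone equal to ASI MOMMY, halfway, or equal to placebo. Gains are normal, mildly skewed (gamma shape 8) or strongly skewed (gamma shape 2). The normality test is Shapiro-Wilk at 0.05 in each arm, and the rank branch is taken if any arm fails. There were 20,000 simulated trials per scenario.

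**Step 1: thresholds.** ANOVA branch: 0.05/3 = 0.0167. Rank branch: 0.05 after a significant Kruskal-Wallis test. The second is a reading of the text, not a stated figure.

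**Step 2: how often the switch changes the ASI MOMMY versus placebo verdict**, compared with always using ANOVA with Bonferroni:

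| Gains | Trials sent to rank branch | Verdict changed |
|---|---|---|
| Normal | 14% | 1.4-1.9% |
| Gamma shape 8 | 33-34% | about 6% |
| Gamma shape 2 | 77% | 14-20% |

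If pooled residuals are tested instead of each arm, normal data switch in only about 5% of trials and about 0.5-1% of verdicts change. Hence 0.5-2% for normal gains.

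**Step 3: direction under strong skew.** With both active arms at 1.05 SD, the chance of significance rises from 0.659 (always ANOVA with Bonferroni) to 0.821, a net gain of 0.162, while 0.169 of verdicts change. Changes towards significance are (0.169 + 0.162)/2 = 0.1655 and changes away are 0.0035. Nearly all go towards significance, for an effect that is real in the simulation.

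**Step 4: source of the changes.** With 0.0167 on both branches, 10-12% of verdicts still change at shape 2. In the scenario of step 3 the figure is 0.116 of 0.169, or 69%. Most changed verdicts thus come from the rank test itself. The unequal threshold still matters for net power there: 0.659 to 0.730 from the rank test (7.1 points), then 0.730 to 0.821 from the looser threshold (9.1 points).

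**Step 5: false positives.** With no differences between arms, the chance of at least one significant pair by Mann-Whitney is:
- behind a significant Kruskal-Wallis test: 4.5-5.0%;
- without that gate: about 11-13% (three independent tests would give 1 − 0.95³ = 14.3%).

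For the whole two-branch procedure with the gate it is 4.4% (normal), 4.5% (shape 8) and 5.4% (shape 2). If only domperidone works, by 1 SD, ASI MOMMY versus placebo is falsely significant in 2.1% (normal) and 4.3% (shape 2).

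**The case against.** The strongest reply is that the error rate is under control. Post hoc tests ordinarily follow a significant overall test, and with exactly three groups that gate holds family-wise error near 5% without Bonferroni. This stands. A reader might infer from the missing correction that the rank branch inflates type I error to about 11-13%. That requires running the pairwise tests whatever Kruskal-Wallis shows, which is the less natural reading. The gate is not stated, but its absence is not stated either.

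Second, no section gives 0.05 as the Mann-Whitney level. A statistical analysis plan, not shown here, may set the level, the gate and the normality test. This also stands, so the 0.05 should be called a reading. It does not remove the point: the protocol itself prescribes the data-driven switch, and an analysis plan that follows it inherits the switch.

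Third, the changes under skew are mostly power gained for a true effect, not false claims, and most would occur at equal thresholds. Correct: this is inconsistency, not bias towards a false benefit.

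Fourth, a reader might call Bonferroni over all three pairs an error, because domperidone versus placebo does not involve ASI MOMMY. It is only conservative, and comparing a declared positive control with placebo is legitimate.

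Finally, section 8.a calls this a pilot. That lowers the stakes, although section 14 still sets a formal test.

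**Conclusion.** The point holds as a minor one. The plan lets an unspecified normality test on groups of 15 choose the analysis of its only stated outcome, and the pairwise comparisons are handled differently on the two branches. The effect on the ASI MOMMY versus placebo verdict is small if gains are near normal and becomes material only if they are markedly skewed. The protocol gives nothing from which to judge which case applies. The sizes rest on the assumed effects, distributions and Shapiro-Wilk rule. That the data choose the test, and that a correction is named on one branch only, rests on the text alone. A general claim of inflated type I error is not supported.

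**What to change.** - Remove the normality-test switch from section 14 and the synopsis.
- State that ASI MOMMY versus placebo on 7-day infant weight gain decides H1.
- Analyse it with one prespecified three-arm linear model adjusted for baseline infant weight, which section 13 already collects, and report the difference with a 95% confidence interval.
- Keep the Kruskal-Wallis and Mann-Whitney analysis as a sensitivity analysis.
- State one multiplicity rule for the confirmatory ASI MOMMY comparisons, whichever test is used: a fixed order (placebo, then domperidone) or an equal split at 0.025 each, at the sponsor's choice.

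If the two branches are kept, the least repair is one sentence that either states the Kruskal-Wallis gate or corrects the Mann-Whitney tests. That would settle the error rate but leave the data-driven choice of test.

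The cost is analysis wording only, with the same data and software. There are trade-offs. Under a fixed order, the domperidone comparison is confirmatory only if the placebo comparison succeeds; under a split, the placebo comparison is tested at 0.025. If gains are strongly skewed, a mean-based analysis loses some power to a rank test at the same alpha (about 81% against 87% at 1.05 SD, gamma shape 2, from an unadjusted t test and Mann-Whitney at 0.05). A sponsor who expects such skew could prespecify the rank test instead. The gain from baseline adjustment is modest: the error variance relative to the simple change score is (1 − ρ²)/(2(1 − ρ)), which is 0.90 at an assumed correlation of 0.80 and 0.975 at 0.95.

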## 9. STUDY POPULATION

### a. Subject Recruitment

Data collection is done by healthcare providers on duty. Data collection is conducted starting from July 2022 until December 2022 by finding information about mothers in labor from Jfestis and Tegalrejo public health centers. Women in

puerperium who meet the inclusion and exclusion criteria are gathered in the research until the number of samples needed is fulfilled.

The researcher explains the research intent, method, and procedure that will be done to the mother. Then the mother is allowed to sign the informed consent form if they agree to become a research subject. The research subjects are given lactation counseling. Next, the research subjects are randomized by the researcher using the random number table with each group containing 15 subjects. The researcher will allocate each group with one type of treatment, that is drug A, drug B, and drug C, then randomization is conducted. The list of randomizations is kept by the researcher.

b. Populasi

The subject population in this research are postpartum women from Tegalrejo Public Health Center and Jetis Public Health Center in Yogyakarta who plan to breastfeed their baby.

c. Inclusion Criteria

- a. Gestational age 37-40 weeks at labor
- b. Giving birth vaginally
- c. Normal body mass index (BMI 18.5-24.9 kg/m^2)
- d. Does not consume drugs or supplements to enhance breastmilk
- e. Healthy women with normal nipple condition (protrudes)
- f. Condition of baby is health with good suction reflex
- g. Baby currently only consumes breastmilk

d. Exclusion Criteria

- a. Allergy towards ASI MOMMY® and Domperidone
- b. Women who consumes drugs that influences the effects of domperidone (such as antacids, cimetidine, ranitidine, famotidine, and nizatidine) or drugs that interacts with domperidone (such as haloperidol, lithium).
- c. Women who are in sick condition and needs in-hospital treatment
- d. Women with HIV AIDS, heart problems, mastitis, and a history of breast surgery
- e. Underweight, overweight, and obese women
- f. Twin pregnancies
- g. Babies born with a congenital disease that affects the breastfeeding process
- h. Babies and mothers who do not follow the regimen from start to finish (seventh day of intervention)

e. Number of CTP Sites

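### The correlations of external variables with weight gain leave out treatment arm, and section 14.d garbles which data get Pearson (minor)

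*Protocol*

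**What the plan says.** The protocol states the rule for external variables twice.

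- Synopsis, Statistical Analysis: "The analysis test for external variables with parametric data and dependent variables was carried out with the Pearson correlation test", and "while for non-parametric data it was carried out with the Spearman correlation test".
- Section 14.d, Significance Testing: "Analytical test for variables aside from parametric data and dependent variables is using Pearson correlation, while non-parametric data is analysed using Spearman correlation".

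The dependent variable is the change in infant weight from day 0 to day 7 of the intervention: "Breast milk production was measured by assessing the infant's weight gain". Mothers are "randomized by the researcher using the random number table with each group containing 15 subjects", so 45 babies in three arms enter the analysis. The comparison between arms is a separate step. For normally distributed data it "is the One Way Anova test with Post Hoc Bonferroni"; otherwise it is Kruskal-Wallis with Mann-Whitney.

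Neither statement of the rule says whether the correlation is pooled over arms, run within each arm or adjusted for arm. Neither lists the external variables or says when they are measured.

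**The concern.** There are two separate matters.

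**Wording.** Taken literally, 14.d withholds Pearson from parametric data, and its second clause gives non-parametric data to Spearman. Parametric data would then have no test. The sentence also no longer refers to external variables, and it does not make clear that the dependent variable is one half of each correlation.

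**Method.** A Pearson or Spearman correlation between two variables has no place for treatment arm. The endpoint in section 14.a expects greater weight gain with the study product, and the sample size in 14.b rests on unequal group means. If the 45 babies are pooled, the spread between arm means counts as unexplained variation in weight gain, and a real association with a baseline variable looks weaker than it is.

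What is at stake is the plan's secondary look at other influences on weight gain, in a study that section 8.a calls a pilot. The efficacy conclusion is not at stake.

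**Working it through.** **The plan's own figures.** The protocol gives no figure for the correlations. Its one design figure is 15 per group, and this cannot be reproduced because section 14.b gives no value for the combined standard deviation. An arm effect must therefore be assumed. One anchor is the effect that a three-group F-test detects with about 80% power at 15 per arm and "Alpha = type 1 error 0,05". A noncentrality of 10.21 gives f = sqrt(10.21/45) = 0.476, with exact power of 79%. The printed means 3426.6, 3221.1 and 3000, with 3000 taken as the third group's mean, would need an SD of about 363 for 80% power, which again gives f of about 0.48. That agreement is not independent support, because the SD was solved for. The printed means are also body weights, not gains.

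**Inputs.** 3 arms of 15; f = 0.476 in units of the within-arm SD (assumed); two-sided 5% test (sidedness assumed); within-arm r as shown (assumed). The pooled correlation has 45 - 2 = 43 degrees of freedom. With arm in the model there are 45 - 4 = 41.

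**Case A: the variable has the same expected value in every arm (measured before treatment).** Pooling multiplies the variance of weight gain by 1 + f² and leaves the covariance unchanged:

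pooled r = r / sqrt(1 + f²) = 0.40 / sqrt(1.227) = 0.361.

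Simulation results:

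| Arm effect on gain | True within-arm r | Pooled: mean r, % significant | Arm-adjusted: mean r, % significant |
|---|---|---|---|
| f = 0.476 | 0.40 | 0.36, 70% | 0.40, 77% |
| 0 / 0.5 / 1 SD | 0.40 | 0.37, 72% | 0.40, 78% |
| 0 / 1 / 1.5 SD | 0.40 | 0.33, 63% | 0.40, 78% |
| 0 / 0.5 / 1 SD | 0 | 0.00, 4.9% | 0.00, 4.9% |
| none | 0.40 | 0.40, 80% | 0.40, 78% |

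There is dilution but no false association, and when the arms do not differ the arm term costs about two points of power.

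**Case B: the variable also shifts with arm, in the same pattern and by the same f = 0.476.**

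- True r = 0: pooled r = f² / (1 + f²) = 0.227 / 1.227 = 0.185. In simulation the mean is 0.19, significant in 23% of trials against 5% with arm in the model.
- True r = -0.30: pooled r = (-0.30 + 0.227) / 1.227 = -0.06. In simulation the mean is -0.05, significant in 5% of trials against 51% with arm in the model.

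**Which case the protocol describes.** The time and event table ticks medical history and the physical examination at screening/baseline only, and section 10.e describes a demographic interview at baseline. These belong to case A. Section 13 leaves open whether blood pressure is read a second time. Section 8.b says that adherence is watched during treatment, but nowhere is it named as an external variable.

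**The case against.** The strongest reply has four parts.

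- **Pooling is inferred.** The text is silent, and whether a secondary correlation is run by arm or adjusted is often left to a statistical analysis plan, which is not shown here. This stands as a caution. Pooling is still the ordinary reading of a plain two-variable correlation, since the protocol asks for figures by group elsewhere (the categorical summaries) and does not do so here.
- **No general leak.** A reader might infer that treatment differences carry over into every one of these correlations and produce false findings at rates such as 23%. The documents do not support that. It requires an external variable that itself differs by arm: one altered by treatment after randomisation, or one with a chance imbalance in the trial at hand. The protocol names none, and most of what it collects is pre-treatment. Randomisation keeps the error rate for such variables at about 5% over repeated trials. The masking figure further requires a true correlation opposite in sign to the one treatment induces. This part of the reply stands in full.
- **The wording is a slip.** The second clause of 14.d and the synopsis show that Pearson was meant for parametric data, and an analyst is unlikely to follow the literal text. This stands: the mismatch is clerical. The two places still need to agree.
- **The treatment comparison is untouched.** This also stands, and it settles the weight of the point.

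What remains is a method that does slightly worse than an equally simple one whenever the arms differ as the trial expects.

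**Conclusion.** The point holds as a minor one. Section 14.d misstates the synopsis rule on which data get Pearson, and neither place brings treatment arm into the correlations.

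The harm the documents support is mild dilution for pre-treatment variables: r of 0.40 is seen as about 0.36, and power drops from about 77% to 70%. Over the other two arm effects tried, pooled r is 0.33 to 0.37 and power 63% to 72%. These figures rest on pooling over all 45 babies and on assumed effect sizes, because the protocol gives no SD. If the arms do not differ, there is no dilution.

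False or masked associations are a conditional risk that depends on which external variables are used, and the protocol does not say. The ANOVA or Kruskal-Wallis comparison of the arms is unaffected.

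**What to change.** 1. Carry the synopsis wording into section 14.d, so that both places give the same rule for parametric and non-parametric external variables against weight gain.
2. Name the external variables and state whether each is measured before or after randomisation.
3. Replace the plain correlations by a linear model of 7-day weight gain on treatment arm plus one external variable at a time, reporting the slope with its 95% CI. Where ranks are preferred, use a partial rank correlation given arm.
4. Label these results exploratory.

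The cost is wording in two places. The data do not change, and such a model is routine in the kind of software the plan already uses. It takes two more degrees of freedom (41 instead of 43). If the arms turn out not to differ, power for r = 0.40 is about 78% instead of 80%.
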